1. For participants who report being in a relationship, what is the impact of the on-demand delivery (treatment) compared to the in-person delivery (counterfactual) of the TYRO Couples curriculum on **marriage/intimate partner relationship behaviors** six months after program enrollment?
2. For participants who report being in a relationship, what is the impact of the on-demand delivery

¹ Source: Chou, S., & Liu, C. (2005). Learning effectiveness in a web-based virtual learning environment: A learner-control perspective. *Journal of Computer Assisted Learning*, 21(1), 65 - 76.

(treatment) compared to the standard in-person delivery (counterfactual) of the TYRO Couples curriculum on **marriage/intimate partner relationship attitudes** after program completion?

3. Primary and secondary outcome measures

For this impact evaluation study, the intervention that will be tested is the delivery format of the TYRO Couples curriculum. The research questions are framed to determine if program participants who are randomly assigned to the TYRO Couples curriculum through an on-demand format will derive more benefits compared to those who are assigned to the TYRO Couples curriculum in a standard, in-person format.

Primary research questions are applicable to the entire population in the study and will be measured six months after the intervention has ended. This study focuses on employment and financial attitudes as the primary research questions. Finding and maintaining a job, which is one of the top priorities participants will have after release, has been noted in criminal justice research to reduce former prisoners' chances of reoffending (Visher, Debus, and Yahner, 2008). Subsequent secondary research questions focusing on relationships are only applicable to the study population who report being in a relationship. However, all research questions are relevant to the TYRO Couples Curriculum as well as consistent with the study's logic model.

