Outcome measures in this study were created for this evaluation and are not based on already-validated scales. Using the local evaluation baseline survey, we will generate a correlation matrix between items in a given construct to ensure that theoretically related items are also empirically related in our data set. Items that are not strongly correlated with other items in a construct will be removed as necessary. Factor analysis will be used to ensure that all construct items hang together (using an alpha of 0.60 or higher as the threshold). We will then create a composite measure by taking an average of the scores on each non-missing item in the construct. For composite measures, a change score will be calculated between a participant's pre-program composite score and six-month-post-enrollment follow-up composite score. If construct items do not meet the 0.60 threshold, that outcome will be removed. An alpha value of 0.60 is the minimally acceptable value that will be used for scale construction.

We will create a composite score by taking the average of multiple individual items. For these composite measures, our plan is to use 20% as a threshold for allowable missing items. This plan is contingent on the final distribution of missing data in our dataset. With a 20% threshold, if a respondent is missing more than 1 item used for creating the employment construct or more than 2 items for creating the financial construct, the respondent will be assigned a missing value for that construct. We will not impute truly missing values for outcomes. To create a construct score, the average will be divided by the number of non-missing values in the construct.

Table 1. Description of outcome measures used to answer impact analysis primary research questions

Research question #	Outcome name	Description of the outcome measure and its properties	Source of the measure	Timing of measure
1	Employment Attitudes	
The outcome measure is a scale (value range of 1=strongly disagree to 5=strongly agree) calculated as the average of eight survey items related to employment attitudes.
 
Sample item: I have the skills I need to get a decent job.
	Local evaluation follow-up-survey	Six months after program enrollment

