Wave 3 of data collection, which includes the local evaluation 6-month post-enrollment follow-up survey, is intended to be collected six months after program enrollment, with data collection efforts focused on five to seven months after program enrollment. However, the timing of the follow-up survey data collection can vary, with some participants taking the survey later than expected (e.g., an email with a survey link is opened and completed months after it was delivered) or earlier than expected (in the case of Franklin CBCF participants who complete their follow-up survey immediately upon release; see below). The tracking process typically begins at least 60 days prior to when a participant is due for a follow-up survey. This allows time for new contact attempts when email addresses are undeliverable and mailings are returned to the sender. The incarcerated population also tends to be a difficult population to get in touch with for various reasons. Someone just released from prison may be focusing on housing and employment needs or their contact information is outdated since they were enrolled into the program.

Waves 1 and 2 of all surveys are administered on paper with participants in person, due to technology restrictions in the prison facilities. Paper surveys are entered onto nFORM and Qualtrics (for the local evaluation surveys) within 72 hours of completion by RIDGE staff who have been certified in protecting human research participants. Paper surveys are securely transported by program staff to the RIDGE offices where they are entered and kept in locked storage.

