The process for follow-up data collection (Wave 3) differs from the other two waves. The MER survey tracking team begins attempts to contact study participants approximately five months after program enrollment using email and text messages as the primary contact methods. Participants are sent a QR code and hyperlink that directs them to the self-administered formatted follow-up survey accessed through Qualtrics. Participants can also complete the follow-up survey over the phone with a member of the MER survey tracking team if they prefer. If initial contact attempts are not successful, the survey tracking team will reach out to secondary contacts that participants have identified and provided contact information for during the study enrollment process. Contact attempts continue for 60 days (until 7 months after program enrollment), after which point the survey tracking team stops efforts to collect follow-up surveys. At this point, program staff are provided a list of participants that the tracking team is

unable to get in contact with. If program staff come in contact with any of the participants on the archived list, they will direct the participants to the follow-up survey. Otherwise, all tracking efforts are complete at that point. All participants who complete a follow-up survey receive a \$50 incentive.

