	Survey Wave 3 (Local evaluation follow-up survey)	Six months after program enrollment; Between three to six months after program enrollment at Franklin CBCF	Online via a QR code or email link; over the phone; in person paper survey if in the eligible Franklin CBCF group	MER Staff or RIDGE facilitator if in the eligible Franklin CBCF group	October 2023 – May 31, 2025 for all locations aside from Franklin CBCF; For Franklin CBCF- May 2024- May 31, 2025

Study group	Data source	Timing of data collection	Mode of data collection	Party responsible for data collection	Start and end date of data collection
Counterfactual (in-person)	Survey Wave 1 (nFORM baseline and local evaluation baseline surveys)	Immediately following informed consent and randomization during orientation	In-person paper survey	RIDGE Staff	April 11, 2023 (or January 2023 for pilot cohort) - November 30, 2024
	Survey Wave 2 (nFORM exit and local evaluation post-surveys)	Six weeks after program enrollment, immediately following the last primary workshop session	In-person paper survey	RIDGE Staff	May 23, 2023 (or February 2023 for pilot cohort) – January 11, 2025
	Survey Wave 3 (Local evaluation follow-up survey)	Six months after program enrollment; Between three to six months after program enrollment at Franklin CBCF	Online via a QR code or email link; over the phone; in person paper survey if in the eligible Franklin CBCF group	MER Staff or RIDGE facilitator if in the eligible Franklin CBCF group	October 2023 – May 31, 2025; For Franklin CBCF- May 2024- May 31, 2025

3. CONSORT diagram

The CONSORT diagram for this impact study (where random assignment occurs after consent) can be found in the appendix to this plan. The data used to complete the CONSORT diagram were pulled on July 22, 2024.

D. Analysis

This section describes the plans for defining the analytic sample, assessing baseline equivalence, cleaning data, handling missing data, and addressing potential crossover and contamination. It also describes the analytic models for estimating program impacts and planned sensitivity analyses.

1. Data preparation

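### The plan gives the primary outcomes three different time points, so the pooled arm effect is an average over survey times and not, without a further assumption, a six-month effect; the text may also tie one six-week secondary outcome to the Wave 3 survey

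*Combined protocol and SAP*

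**What the plan says.** **Primary time point.** Research questions 1 and 2 and Table 1 give the timing of employment and financial attitudes as "Six months after program enrollment". Section A.3 (Primary and secondary outcome measures) says that the primary research questions "will be measured six months after the intervention has ended". Table 5 gives Wave 3, in both arms, as "Six months after program enrollment; Between three to six months after program enrollment at Franklin CBCF".

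**How Wave 3 is collected (section C.2).** Wave 3 is aimed at six months, "with data collection efforts focused on five to seven months after program enrollment". The text expects exceptions in both directions:

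- Late: for example, "an email with a survey link is opened and completed months after it was delivered". Active contact stops at seven months. If staff later meet someone on the archived list, "they will direct the participants to the follow-up survey".
- Early: "in the case of Franklin CBCF participants who complete their follow-up survey immediately upon release". Franklin enrols about 78% of the study. The early paper route is for those joining a jobs initiative and starts in May 2024. Their share is not given.

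Section C.2 also says that the process and timing of data collection are the same in both arms.

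**Analysis.** Section D.3 and Table 6 enter days from enrolment to the follow-up survey as a covariate for every outcome, with no arm-by-time term. A facility indicator is only to be considered. Section D.4 repeats the analysis among those surveyed at 5-7 months, because of the Franklin change.

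**Relationship attitudes.** Table 2 takes this secondary outcome from the post-survey (Wave 2), which section C.2 places at six weeks. Section D.1 excludes those who do not respond at the follow-up time point. Section D.2 requires a value at baseline and follow-up for the construct.

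**The concern.** The headline result will carry a time label. If it is reported as a six-month effect, part of it will come from answers given from about three months, at or just before release. Section A.3 justifies the employment outcome by what happens after release, so whether the arm difference is the same before and after that transition is a substantive question. The plan shows that timing varies, but does not say what must hold for the pooled coefficient to keep its six-month label.

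For relationship attitudes, a term measured after the outcome, and known only for people who completed a later survey, would enter the model. Participants with complete baseline and Wave 2 data would be dropped for lack of Wave 3, with no analytic gain.

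**Working it through.** **1. Does the intervention-end anchor fit the calendar?**

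- Six weeks = 42 days = 42/30.4375 = 1.38 months, so six months after the end is 6 + 1.38 = 7.38 months after enrolment. Active contact stops at 7.
- Table 5: Wave 1 ends November 30, 2024. Adding 42 days gives January 11, 2025, which is the stated Wave 2 end. Adding six months gives July 11, 2025, which is 41 days after Wave 3 closes on May 31, 2025.
- Anchored on enrolment, November 30, 2024 plus six months is May 30, 2025, inside the close.

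The enrolment anchor fits the plan's dates and the intervention-end anchor does not.

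**2. What does the pooled coefficient estimate?** Write the arm effect at survey time t as d(t). A timing term without an interaction adjusts the level of the outcome, not d(t). If survey times have the same distribution in both arms, as section C.2 intends, the arm coefficient is the mean of d(t) over the survey times that occur. That equals d(6) if d is constant, or if d is linear and mean survey time is six months. Neither condition is stated.

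**3. How far off could it be?** The documents give neither the early share nor the shape of d(t), so what follows is illustration. Assumptions: Franklin supplies 78% of surveys (its enrolment share); a fraction f of these are early, spread evenly over 3-6 months (mean 4.5); all others are spread evenly over 5-7 months (mean 6); d(t) = 0.20 × (6 − t)/3, that is 0.20 SD at three months, 0 at six, and on the same line after that.

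| f | Early share 0.78f | Mean time 6 − 1.5 × share (months) | Pooled effect 0.20 × (6 − mean)/3 | d(6) |
|---|---|---|---|---|
| 0.25 | 0.195 | 5.71 | 0.020 | 0 |
| 0.50 | 0.390 | 5.42 | 0.039 | 0 |

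The departure is about 0.02-0.04 SD. If the effect instead rose from 0 at three months to 0.20 at six, the pooled value would fall short of 0.20 by the same amounts. Late surveys pull the other way: if 5% of the non-early surveys came at 7-10 months (mean 8.5), the non-early mean would be 6 + 0.05 × 2.5 = 6.125, the overall means 5.81 and 5.49, and the departures about 0.01 and 0.03.

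**4. What does the 5-7 month analysis cost?** The detectable effect grows by √(1/share kept). For f = 0.25 and 0.50:

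- Early surveys even over 3-6 months, so two thirds fall before month 5: kept 0.87 and 0.74, ratios 1.07 and 1.16.
- All early surveys before month 5: kept 0.805 and 0.61, ratios 1.11 and 1.28.

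The loss is 7-28% before any late surveys are removed. The plan states no alpha or power. Assuming two-sided 5%, 80% power, equal arms and no covariate gain, 2.80 × √(4/n) gives 0.202 SD at the target of 768. At n = 668 to 468 it gives 0.217 to 0.259 SD.

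**5. Relationship attitudes, texts side by side.** The outcome is a Wave 2 score at about six weeks. The covariate in Table 6 is days to the follow-up survey, and section C.2 uses follow-up for Wave 3 only. Table 6 limits relationship status to certain outcomes but not the timing term. Read literally, the covariate is missing for anyone without Wave 3, and section D.1 excludes them in any case. Figure A.3 shows Wave 3 completion of (64 + 52)/(206 + 190) = 116/396 = 29.3% at July 22, 2024.

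**The case against.** The strongest reply is that the plan already handles timing. The variation is disclosed in several places, days to survey is a covariate, and the 5-7 month analysis was added because of Franklin. Under the trend in step 3 the departure is small beside a 0.20 SD detectable effect. This stands to the extent that no new primary model is needed. What remains is a contradiction about the time point and a missing statement of what the pooled estimate means.

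A reader might infer more, in ways the documents do not support:

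- **That the arms are compared at different times, so the contrast is biased.** Wave 3 procedures are the same in both arms.
- **That 78% of surveys are early.** Table 5 reads as if all of Franklin were, but section C.2 limits the early route to invited jobs-initiative participants from May 2024. With every Franklin survey early, step 3 would give 0.10 × 0.78 = 0.08 SD.
- **That a constant effect is the only assumption that rescues the label.** A linear trend with mean survey time near six months also does.
- **That surveys after seven months are scheduled.** They are accepted, but active contact has stopped.
- **That about 71% of the relationship-attitudes sample would be lost.** That projects an interim completion rate, largely from before the new Franklin procedure. The final loss cannot be bounded from the documents.

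On relationship attitudes, section D.2 speaks of time points for the construct, section D.1 lists post-survey nonresponse separately, and section D.5 extends the primary approach to relationship behaviors only. Follow-up may therefore mean each outcome's own wave. If so, only the wording needs correcting. Section D.3 does name relationship attitudes when it lists covariates, so the literal reading remains open.

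**Conclusion.** The point holds as a problem of definition and labelling. The plan states the primary time point in three ways, and one of them does not fit its own calendar. The pooled coefficient is an average effect over actual Wave 3 times, and calling it a six-month effect needs an assumption that the plan does not state. The size of any departure is unknown. The 0.02-0.04 SD figure rests wholly on the assumed trend and early share.

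The relationship-attitudes point is conditional. On the literal reading a six-week outcome is restricted to Wave 3 responders; on the own-wave reading it is a wording correction. It concerns one exploratory outcome in a set that the plan already calls underpowered.

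Both should be corrected before analysis. Neither prevents the analysis from going ahead.

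**What to change.** 1. Reconcile the research questions, section A.3, Tables 1, 2 and 5, and section C.2 to one description anchored on enrolment. Report the pooled estimate as the average effect at the Wave 3 survey, intended at six months and partly earlier at Franklin. If it is called a six-month effect, state the assumption beside it.
2. Tabulate survey timing (before month 5, months 5-7, after month 7) by arm and site. Show the planned 5-7 month estimate next to the pooled one, noting that it selects on a variable observed after randomisation and is less precise.
3. For relationship attitudes, use days to the Wave 2 post-survey or no timing term. State in sections D.1 and D.2 that its sample needs baseline and Wave 2 data, not Wave 3.

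The cost is wording, one table and a less clean headline time point. No new data and no new primary model are needed.

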Because technology restrictions in prison facilities require the administration of paper surveys, it is possible for respondents to answer questions in violation of skip/display logic if they misunderstand the instructions on the paper survey. To err on the side of retaining as much of the sample as possible, we will not deem a response invalid if the participant response to a skip logic question incorrectly (answering "no" instead of "yes") but then proceeds to answer the follow-up question accurately.

Participants who report inconsistencies in the number or age of their child(ren) between nFORM and local evaluation surveys at the same time point will have their answers be assigned as the response they gave on the nFORM ACS or entrance survey.

Outlier values, defined as extremely low or extremely high values that are likely introduced to the dataset due to an input error, for variables such as participant's age, children's age, and income, which participants manually input, will be recoded to the 99th percentile for the sample if necessary. We will top-code any values above the 99th percentile with the average of all values below this threshold.

Duplicate data

In the case of duplicate data, where one participant has taken the same local evaluation survey more than one time, we plan to take the following approach:

- Check for incorrectly entered Client IDs that inaccurately flag surveys as duplicates. Using the name and/or DOB fields on the local evaluation survey, we will check that responses that appear to be duplicates were in fact collected from the same participant multiple times (i.e., are true duplicates). Common instances of this occurring could be if a participant did not finish a survey and re-took it later on, or if they took the follow-up survey twice for the incentive. If the survey is not a true duplicate, we will correct Client IDs as necessary.
- For surveys identified as true duplicates, we will check for completeness. If one duplicate survey is complete while the other is not, we will use the most complete survey to minimize item non-response.
- If both duplicate surveys are equally complete, we will use the first response that a participant submitted, as indicated by the Recorded Date field on the Qualtrics data export. This approach is

only applicable to the follow-up survey. Because program staff enter paper survey data into Qualtrics, there should not be duplicate baseline and post-surveys.

Missing data

Survey nonresponse

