All outcome measures for this study are constructed averages calculated using a number of theoretically and empirically related survey items. As mentioned in the previous section, a respondent who answers some but not all survey items in a given outcome construct will have their outcome value assigned as missing if they do not respond to at least 80% of the items in the construct. We will not impute missing baseline or outcome data for our analyses. Based on the recommendation from ACF, we will use the cautious attrition threshold from the What Works Clearinghouse (WWC) to assess whether attrition can be considered high or low.

Assessment of baseline equivalence

Per the WWC's standards, we will use effect sizes (i.e., standardized mean differences), to examine the baseline equivalence between the study groups. Effect size is defined as the difference between the intervention group mean and the comparison group mean, divided by the pooled standard deviation. We will calculate the effect size for demographic characteristics (such as gender, age, and race/ethnicity, as reported on the nFORM Applicant Characteristics Survey) and each baseline outcome of interest depending on the type of variable: Hedge's g , for continuous variables; and Cox's index, for dichotomous variables. We can determine baseline equivalence by comparing each outcome's effect size using the WWC standard, which suggests that if the corresponding effect size is 0.05 or less in absolute value, it is considered "small," and we can conclude that it satisfies baseline equivalence without statistical adjustment. However, if the effect size falls between 0.05 and 0.25, it is considered "moderate," and it will require a statistical adjustment to meet baseline equivalence (we will use statistical adjustments such as regression adjustments or matching/weighting). Lastly, in the case that the effect size is greater than 0.25, it will be considered "large", which shows that the differences at baseline are too large to meet WWC standards, even with statistical adjustments. In that case, we will apply appropriate caveats to any interpretation of the results.

Condition crossover

At the primary RCT enrollment site, Franklin CBCF, condition crossover is not possible due to restrictions put in place when designing the implementation of the two delivery formats. If a participant who was

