Analyses will be conducted using the R Studio statistical software package. The basic model for this impact evaluation will include a dummy variable for intervention group assignment, equal to 1 if a participant was randomly assigned to receive the curriculum on-demand via tablet, and a participant's score at baseline as the main predictors of each outcome measure at follow-up. To enhance the precision of the impact estimates, we plan to include several other covariates in our models. For all outcome analyses, we will control for participant age, gender, and race, as well as the timing of a participant's follow-up survey (number of days between program enrollment and follow-up survey completion). We will also consider including a facility indicator to denote which site the participant received services at. Additionally, we will include any demographic variables that were shown to be significantly different between study groups during baseline equivalency analysis. For the healthy relationship attitudes outcome, we also plan to include relationship status at baseline as a covariate. This will only be available if a participant reports being in a relationship at baseline and at follow-up.

Table 6. Covariates included in impact analyses

Covariate	Description of the covariate
Age	Age (in years) as of the baseline data collection, as reported on the ACS
Gender	Self-reported gender identification as of the baseline data collection, as reported on the ACS
Race	Self-reported racial identification as of the baseline data collection, as reported on the ACS

Covariate	Description of the covariate
Timing of follow-up survey	Number of days between program enrollment date and date of follow-up survey completion to control for variation in survey timing
Relationship status (relationship attitude and behavior outcomes only)	Relationship status (1 = in a committed relationship, 0 = not in a committed relationship) as of the baseline data collection, as reported on the ACS

4. Sensitivity analyses for primary research questions

We plan to conduct several sensitivity analyses to test the robustness of our results. First, and as mentioned earlier in the plan, we will conduct a sensitivity analysis to see if and how our outcome construct measures change if we use 70% as a threshold for non-missing items instead of 80% as a threshold.

[figure not shown]

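### The two outlier sentences conflict: one sends low errors to the 99th percentile, the other overwrites correct high values with the mean

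*Combined protocol and SAP*

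**What the plan says.** The rule stands in section D.1, under the heading on inconsistent or seemingly inaccurate data, as two consecutive sentences.

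- The first concerns entries that respondents write in themselves, with their own age, the ages of their children and income as the examples. It sets the scope as "Outlier values, defined as extremely low or extremely high values that are likely introduced to the dataset due to an input error". The plan says that these "will be recoded to the 99th percentile for the sample if necessary". No lower percentile is named.
- The second reads: "We will top-code any values above the 99th percentile with the average of all values below this threshold".

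Of the three variables named, age is the only one with a stated use in the analysis. Section D.3 says "For all outcome analyses, we will control for participant age, gender, and race", and Table 6 defines the covariate as "Age (in years) as of the baseline data collection, as reported on the ACS". Section D.2, on baseline equivalence, says "We will calculate the effect size for demographic characteristics (such as gender, age, and race/ethnicity". That section treats an absolute effect size up to 0.05 as acceptable without adjustment, one between 0.05 and 0.25 as needing statistical adjustment, and one above 0.25 as too large even with adjustment.

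**The concern.** Two analysts following this text would build different files. For an erroneous high value, one sentence gives the 99th percentile and the other gives roughly the sample mean. For an erroneous low value, the only replacement named is at the opposite end of the distribution. The second sentence also drops the condition that a value be a likely error. Because some values normally lie above the sample 99th percentile, it changes correct data by design.

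At stake are the recorded ages of a few participants, the reported spread of age, and the reported age effect size in the equivalence table. That effect size is judged against a narrow first cut-off of 0.05.

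**Working it through.** The plan gives no figure of its own here, so the check is a comparison of the two sentences followed by an illustration of size.

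**1. The sentences side by side**

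| | First sentence | Second sentence |
|---|---|---|
| Applies to | likely input errors, low or high | any value above the 99th percentile |
| Limit on use | only if necessary | none |
| High value becomes | 99th percentile | mean of the values below it |
| Low value becomes | 99th percentile | not covered |

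No other section says which sentence governs.

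**2. How many values the second sentence reaches**

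The target analytic sample is 768, 384 per group (section C.1). Expected number above the 99th percentile: 0.01 × 768 = 7.68. With ages in whole years, ties at the cut-off lower this slightly; the simulation in step 3 averaged 7.04.

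**3. What the values become**

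The documents give no age distribution, so this is an assumption: normal, mean 36, SD 10, held within 18-75, N = 768, 2,000 replicates.

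- 99th percentile: about 59 years. Mean of the values below it: about 36 years.
- SD of age: 9.67 raw, 9.58 capped at the 99th percentile, 9.32 with mean substitution.
- Read literally, the first sentence would turn an erroneously low age into about 59.

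Three assumed shapes with mean 36, SD about 10 and minimum 18 give this range:

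| Shape | SD, raw to mean-substituted | Cut in SD | Correlation with true age: mean substitution | Capping |
|---|---|---|---|---|
| Truncated normal | 9.6 to 9.2 | 0.4/9.6 = 4% | 0.96 | 0.999 |
| Shifted gamma | 10.1 to 9.3 | 0.8/10.1 = 8% | 0.92 | 0.996 |
| Shifted lognormal | 10.0 to 8.8 | 1.2/10.0 = 12% | 0.88 | 0.987 |

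**4. Effect on the age effect size**

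Effect size = (difference in group means) / (pooled SD). In randomised groups of 384, under the same three shapes, mean substitution gave:

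- an average absolute shift of 0.017-0.028;
- a crossing of the 0.05 line in 14-24% of replicates, against 2-7% for ordinary capping;
- a crossing of the 0.25 line in at most 0.1% of replicates.

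A hand check for the normal case:

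- The mean age fell from 36.15 to 35.90, so each altered record moved by about 0.25 × 768 / 7.04 = 27 years.
- One such record shifts its group mean by 27 / 384 = 0.07 years, or 0.07 / 9.67 = 0.007 SD.
- Seven records split at random between two equal groups differ in number by 2.19 on average (280/128 from the binomial distribution).
- 2.19 × 0.0073 = 0.016, which agrees with the lower end of the simulated range.

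**5. Effect on the treatment estimate**

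A simulated regression used N = 768, an assumed treatment effect of 0.2, and baseline score and age as covariates. The mean estimate was 0.1998 with an empirical standard error of 0.0593 under raw, capped and mean-substituted age alike. This is expected, because a few altered ages in a randomised trial are nearly unrelated to assignment.

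**The case against.** The strongest reply is that this is loose drafting with almost no consequence, and much of that stands.

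- The first sentence is guarded: it covers only likely input errors and acts only if necessary. Its authors probably had high values in mind and left low ones unspecified. The charge of overwriting correct data therefore rests on the second sentence alone.
- Crossing 0.05 only triggers statistical adjustment, and age is already adjusted for in every model. The 0.25 line, where interpretation would change, is almost never crossed.
- The illustrative figures depend on assumed age shapes, and the largest come from the most skewed one.

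What does not stand is the suggestion that ordinary capping is what the plan says. The second sentence specifies a different replacement value, and nothing elsewhere corrects it.

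A reader might go further in two ways that the text does not support. One is to read the sentences as a sequence, recoding first and averaging afterwards. The plan states no order, and a value already set to the 99th percentile is not above it. The other is to count income and children's ages as further damage to the analysis. Neither appears in Table 6 or among the characteristics named for baseline equivalence.

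**Conclusion.** Wrong as written, and minor. The two sentences cannot both be followed for high values, the only value named for low errors is in the wrong tail, and the second sentence alters about 7 or 8 correct or incorrect values in 768 without distinction.

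The consequence is confined to age. Its SD would be understated by about 4-12%, and its effect size shifted by about 0.02-0.03 on average, enough to change the reported side of the 0.05 line in roughly 14-24% of simulated trials. These figures are illustrative and rest on assumed age distributions. The contradiction itself rests on the text alone.

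A reader might infer that the primary result is at risk. The documents do not support that. Both primary outcomes are 1-5 scales built from survey items (employment attitudes is "calculated as the average of eight survey items related to employment attitudes"), not numbers that participants type in, and the simulated treatment estimate did not move to four decimals.

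**What to change.** Replace both sentences with one rule:

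1. Check implausible values against the stored paper form or the date of birth, and correct them.
2. Set impossible values that cannot be verified to missing.
3. Leave plausible values unchanged, however high or low.
4. If any capping is kept, apply the upper percentile to high values only and state a separate lower limit for low values.
5. Delete the replacement by the mean.

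The checks are feasible. Section C.2 says that paper surveys are kept in locked storage, and section D.1 already uses the date-of-birth field of the local survey to resolve duplicates. Follow-up collection runs to May 31, 2025, after the plan's date of August 22, 2024, so on those dates the rule could be settled before the final analysis.

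The cost is two sentences of wording, checking a handful of records, and possibly a few missing ages. Section D.2 rules out imputing missing baseline data, so the revised text should also say how a participant with a missing age is handled in the adjusted models.
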